**A Prospective Randomized Control Trial of The Effectiveness of Entereg as a Rescue Treatment of
Postoperative Ileus Following Colorectal Surgery**

NCT02742181

November 17, 2016

Primary Investigator:
[name]
[name]
[name]
P: [contact]
F: [contact]
[contact]

Co-Investigators:
[name]
[name]
[name]
[name]

Objectives

Primary:

- To determine the efficacy and safety of Entereg for the treatment of post operative ileus following colon or rectal resection.

Secondary

- To determine the effect of Entereg as rescue therapy postoperative ileus on hospital length of stay, return of bowel function, and 30-day outcomes.

Clinical hypotheses

Entereg can be given to patients after the development of post operative ileus to reduce the duration of ileus and shorten hospital stay.

Postoperative ileus (POI) is one of the most common complications following abdominal surgery, and a frequent cause of prolonged hospitalization ¹. The exact mechanisms of POI, defined as the prolonged transient impairment of bowel motility, are not well defined and are likely multifactorial ^{2,3}. The most commonly cited factors leading to the development of POI are disorganized electrical activity, sympathetic inhibitory neural reflexes, release of proinflammatory mediators, excessive intravascular volume, and the use of opioid analgesia ^{4,5}.

A variety of perioperative strategies have been developed to help prevent the development of and/or reduce the duration of POI. These strategies have been incorporated into most Enhanced Recovery After Surgery (ERAS) pathways, and include avoidance of mechanical bowel preparation, use of laparoscopy when feasible, IV fluid restriction, no routine nasogastric tube placement, early feeding and ambulation after surgery, and limiting opioid use ^{6,7}. Several pharmacologic agents have been studied as means to prevent POI. The most successful of these is Entereg, a peripheral opioid antagonist, currently approved for use in open bowel resection. Given preoperatively and continued postoperatively until return of bowel function, Entereg has been shown to reduce the incidence of POI, shorten hospital stay, and is associated with lower postoperative morbidity and readmissions compared to placebo ⁸⁻¹⁰.

Currently there are no effective treatments for POI ileus after it develops.

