This will be a prospective randomized control trial with a total of 142 patients. Patients who undergo laparoscopic or open colorectal resection, small bowel resection, or ileostomy reversal with small bowel resection that subsequently develop postoperative ileus will be eligible for enrollment. If they meet inclusion/exclusion criteria, they will be randomized at the time of diagnosis of postoperative ileus to receive Entereg as rescue therapy or to receive conservative standard care.

Patients randomized to the Entereg group will be given 12mg of Entereg two times daily from the time of randomization until the return of bowel function or 5 days. Both groups will be treated with conservative standard care, including bowel rest, reduction in oral diet, and placement of nasogastric tube as clinically indicated.

All patients will follow a standard ERAS pathway after surgery, with early feeding and ambulation, along with opioid minimizing measures as is our standard postoperative protocol.

Primary outcome will be hospital length of stay.

Secondary outcomes will include time to return of bowel function, 30-day morbidity/mortality, complications, reoperation and readmission.

Total number of patients: 142

Patients in each study group: 71

Inclusion criteria

1. Subjects who have benign or malignant colonic or rectal disease that have undergone laparoscopic or open colorectal resection, small bowel resection or ileostomy reversal with small bowel resection and subsequently developed postoperative ileus, defined as:
 - a. Return to NPO status after initial diet attempts, or
 - b. Placement of nasogastric tube
2. Subjects who are 18 years of age and older
3. Subjects of either gender
4. Subjects who are willing and able to adhere to protocol requirements, agree to participate in the study program and provide written and informed consent.

Exclusion criteria

1. Subjects who received Entereg preoperatively.
2. Subjects that have taken therapeutic doses of opioids for more than 7 days immediately prior to surgery.
3. Subjects with severe hepatic impairment.
4. Subjects with end-stage renal disease.
5. Subjects who are pregnant.

6. Subjects who were diagnosed with a complete small bowel obstruction preoperatively.
7. Subjects with a medical condition that may interfere with the use of the study medication Entereg.

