8. Subjects who have a condition or general disability or infirmity that in the opinion of the investigator precludes further participation in the study
9. Subjects with an ostomy

Study Calendar	Screening	Remaining Hospitalization	30 Day Follow-up
Enrollment Criteria	x	x	
Study Group Assignment	x		
Informed Consent	x		
History and Physical	x		
Collection of demographic data	x	x	
Monitoring for return of bowel function		x	
Administration of Entereg 12mg PO BID or conservative management		x (until return of bowel function)	
Enhanced Recovery Program (ERP)		x	
Complications/ Adverse events		x	x

Recruitment

Patients will be recruited from the University Hospitals Case Medical Center Division of Colorectal Surgery in Cleveland, OH. The patient population in this study will be candidates of either sex, over 18, who have benign or malignant colonic or rectal disease in which resection was performed via an open or laparoscopic approach, small bowel resection or ileostomy reversal with small bowel resection and primary anastomosis and subsequently developed postoperative ileus. The diagnosis of postoperative ileus will be made by meeting one or more of the following criteria: 1) return to NPO status after initial attempts at oral diet, 2) placement of nasogastric tube after surgery. Patients will be recruited until at least 142 participants are enrolled unless the study is halted prematurely by the safety monitoring board. The investigators will discuss the study with potential subjects prior to surgery date. The potential subjects will be given an information sheet to provide information about the study prior to surgery as part of their pre-op packet. This will give patients an opportunity to review information on the study in the event they are diagnosed with an ileus and approached to participate.

Enrollment and Consent

Enrollment will take at the time of diagnosis of postoperative ileus. The patients will be asked to participate in the study after evaluation by either the PI or the co-investigators. The investigator and study coordinator will discuss the study with the patient and informed consent will be obtained. Patients will be assigned a unique study identification number.

Randomization

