Standard discharge criteria will be applied to all patients, including:

- Passage of stool
- Ability to tolerate solid food and to drink comfortably
- Adequate oral analgesia
- Patient's willingness to be discharged.

Data to be collected

The medical/surgical information below will be collected as part of this research study and is all information already available as part of the patients medical chart.

- Patient name, medical record number
- Past Medical History

- Past Surgical history
- Preoperative Medications (including steroids, anticoagulation, opioid use)
- Pre-operative Diagnosis
- Patient Demographics (age, gender, BMI, ASA score)
- Procedure performed
- Time of surgery
- Wound classification
- Estimated blood loss
- Intraoperative transfusion
- Intraoperative IV fluids given
- Conversion from laparoscopic to open procedure
- Stoma creation
- Time/day surgery to ileus
- Time from surgery to medication given
- Time from ileus diagnosis to medication given
- Was there return of bowel function (flatus or stool, solid or liquid, stoma output) prior to ileus
- Intra-abdominal infection/anastomotic leak
- Time/day of return of bowel function post ileus (flatus and stool- solid or liquid, and stoma function)
- Time/day of ability to tolerate oral diet (liquid and solid food)
- Nasogastric tube placement and daily output
- Duration of nasogastric tube
- Use and type of anti-emetics given
- Total number of Entereg doses given
- Post operative complications including reoperation
- Length of stay in hospital, defined as time from surgery to discharge
- 30-day readmissions

The above collected data will be put into a REDCap (Research Electronic Data Capture) database which is a secure web application for managing online surveys and databases. It allows the safe and secure storage of research data including storage of PHI HIPAA identifier fields.

Study Completion

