Completion of participation in the study will be 30 days after the date of surgery. Any readmission up to 30 days post-operatively to the hospital as a direct result of their surgery will be followed. The patients will follow-up with the surgeon in the office in approximately 3-6 weeks, which is considered standard of care for all patients undergoing colorectal surgery and is not considered part of the research study. Any patient for whom follow-up documentation is missing or incomplete shall be contacted via telephone. The purpose of the call will be to simply determine return to function and outcome. Only a co-investigator shall contact the subject and will identify themselves at the beginning of the call. Any subject can reserve the right not to participate in the phone call interview; they would remain in the study.

Patient Withdrawal

A subject has the right to withdraw from the study at any time for any reason without prejudice to their future medical care by the physician or the institution. The investigator and principal site also have the right to withdraw subjects from the study for the reasons listed below. Should a subject (or subject's legally authorized guardian/representative) decide to withdraw or be withdrawn, reasonable efforts will be made to complete and report the observations as thoroughly as possible.

Subjects may be removed from the study, if any one or more of the following events occur:

- Serious Adverse Event
- Noncompliance
- Lost to follow-up
- Investigator/Principal site recommendation

- Withdrawal of consent
- Protocol Violation
- Intercurrent illness
- The investigator considers it in the patient's best interest to do so

This study is estimated to take 24 months for completion.

Statistical Plan

After recruitment of 71 patients, a safety monitoring board comprised of members of the University Hospitals Faculty will evaluate data and adverse events to ensure that there are not ongoing safety concerns that might call for early termination of the study.

Variables/Time Points of Interest

The following data will be recorded as described in the Study Procedures:

- Patient name, medical record number
- Past Medical History
- Past Surgical history
- Medications (including steroids, anticoagulation, opioid use)
- Pre-operative Diagnosis
- Patient Demographics (age, gender, BMI, ASA score)
- Procedure performed
- Time of surgery
- Wound classification
- Estimated blood loss
- Intraoperative transfusion

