- Related (in the investigator's opinion, the event has a 50% or greater chance of being related to the subject's participation in the study), and
- Gives evidence of new or increased risk to subject(s).

A reportable problem may include, but is not limited to, adverse events, protocol deviations, non-compliance, etc. Within 24 hours of knowledge of a reportable problem, the principal site must be notified. It is acceptable for the first notification to be a telephone conversation with the appropriate person at the principal site (leaving

All adverse events will be reported per local IRB policy.

Reportable Problem: Any event which meets all three of the following criteria:

- Unexpected (in relation to the protocol and informed consent document),
- Related (in the investigator's opinion, the event has a 50% or greater chance of being related to the subject's participation in the study), and
- Gives evidence of new or increased risk to subject(s).

A reportable problem may include, but is not limited to, adverse events, protocol deviations, non-compliance, etc. Within 24 hours of knowledge of a reportable problem, the principal site must be notified. It is acceptable for the first notification to be a telephone conversation with the appropriate person at the principal site (leaving a message is not sufficient) as long as the appropriately-completed CRF is submitted in a timely manner following the call.

Adverse Event (AE): Any new, undesirable medical experience or worsening of a pre-existing condition which occurs during study procedure or follow-up. Any and all adverse events, regardless of seriousness, that meet the above definition of a reportable problem, will be reported to the principal site within the timeframes indicated above.

For reportable adverse events, the following will be determined and recorded on the adverse event case report form:

- Onset Date and Resolved Date (unless continuing)
- Intensity/Severity
- Discontinued due to AE
- Relationship to Drug/Procedure
- Action Taken
- Outcome

The following guideline is suggested in determining the severity of each adverse event in this study:

- Mild – event is noticeable but transient, requires no treatment and does not interfere with the subject's daily activities.

- Moderate – event causes a low level of inconvenience or discomfort to the subject and may partially interfere with daily activities, and may require treatment.

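### Complications and reoperations are collected without an onset date although randomisation comes after surgery, so events before and after randomisation cannot be separated from the data as listed

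*Combined protocol and SAP*

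**What the plan says.** Study Overview places randomisation after surgery: for eligible patients, "they will be randomized at the time of diagnosis of postoperative ileus". The same section lists the outcomes: "Secondary outcomes will include time to return of bowel function, 30-day morbidity/mortality, complications, reoperation and readmission". It gives no start point for any of them and no list of what counts as morbidity or a complication.

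The stated clocks run from surgery. Data to be collected defines length of stay as surgery to discharge. Study Completion says "Completion of participation in the study will be 30 days after the date of surgery", and on readmission, "Any readmission up to 30 days post-operatively to the hospital as a direct result of their surgery will be followed".

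Data to be collected, repeated under Variables/Time Points of Interest, has one item for complications, "Post operative complications including reoperation", and one for intra-abdominal infection or anastomotic leak. Neither carries a date or time. In the same lists the ileus, the return of bowel function and the tolerance of diet are all timed.

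Two places point to collection after enrolment. The Study Calendar marks its row "Complications/ Adverse events" under Remaining Hospitalization and 30 Day Follow-up, but not under Screening, where group assignment sits. The adverse event definition covers new or worsening events during study procedure or follow-up. Onset dates appear once, with a limited scope: "For reportable adverse events, the following will be determined and recorded on the adverse event case report form". A reportable event must be unexpected, judged at least 50% likely to be related to participation, and evidence of new or increased risk.

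**The concern.** Surgery comes first, ileus follows, and only then is an arm assigned. A leak, an infection or a return to theatre can fall in the interval between surgery and assignment, and such an event may itself have led to the ileus. It cannot be an effect of an arm that had not been assigned. No exclusion criterion names these events, so such patients can enter, subject to the investigator-judged exclusions.

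A chart abstractor who follows the lists would record that a complication occurred, but not when. Safety is part of the primary objective, and morbidity, complications and reoperation are named secondary outcomes. The trial is open-label, and the co-investigators and research team perform the analysis. If undated events have to be assigned to before or after randomisation at the end, people who may know the arm could be doing it.

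**Working it through.** **The plan's own figures.** The plan gives no complication rate, no reoperation rate and no surgery-to-ileus interval. Its sample size rests on length of stay, so there is no stated figure to reproduce on this point. The 71 patients per arm are used below only for scale.

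**Can the listed data separate the two periods?**

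| Item | Dated in the plan? | Can it precede randomisation? |
|---|---|---|
| Qualifying ileus | Yes, time from surgery is recorded | Yes, always |
| Return of bowel function after ileus, diet | Yes | Not at issue |
| Infection/anastomotic leak | No | Yes |
| Other complications, reoperation | No | Yes |
| Reportable adverse events | Yes, onset date on the form | Defined as new or worsening during the study |
| Death | Not at issue | No |
| Readmission | Not at issue | Effectively no: patients are randomised in hospital |

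The exposed items are infection/leak, other complications and reoperation, and through them morbidity. An ordinary surgical complication that is expected, or not judged related, falls outside the reportable-event form and so has no required date.

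**Size if earlier events are counted.** Let q be the share of patients in each arm with an earlier event, and p the risk of an event after randomisation, with the two independent.

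Observed risk = 1 − (1 − q)(1 − p) = q + (1 − q)p

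Observed difference = (1 − q)(p_control − p_Entereg)

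The values of p and q are assumptions; the documents supply none. With p = 20% on Entereg v 30% on control:

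| q | Entereg | Control | Difference | Risk ratio |
|---|---|---|---|---|
| 0 | 20% | 30% | 10 points | 0.67 |
| 10% | 0.10 + 0.90 × 0.20 = 28% | 0.10 + 0.90 × 0.30 = 37% | 9 points | 0.76 |
| 20% | 0.20 + 0.80 × 0.20 = 36% | 0.20 + 0.80 × 0.30 = 44% | 8 points | 0.82 |
| 30% | 0.30 + 0.70 × 0.20 = 44% | 0.30 + 0.70 × 0.30 = 51% | 7 points | 0.86 |

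**Effect on power** (71 per arm, two-sided 0.05, normal approximation):

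| True risks | q = 0 | q = 10% | q = 20% | q = 30% |
|---|---|---|---|---|
| 20% v 30% | 28% | 21% | 16% | 13% |
| 15% v 30% | 57% | 42% | 31% | 24% |

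q is expected to be the same in both arms because it is fixed before randomisation. The effect is therefore dilution, with some added chance imbalance, and not a shift towards either arm.

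**The case against.** The strongest reply is that the plan is silent here rather than wrong. No sentence starts the complication outcomes at surgery. Study Completion fixes when participation ends, and an end date is not a start date. Read with the calendar, it gives a coherent window from assignment to day 30 after surgery. The adverse event definition also leaves out earlier events unless they worsen. All of this stands, so the plan cannot be said to count earlier events as outcomes or to contain two contradictory windows.

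A reader might also infer that every patient enters with a complication already scored, which would make any-complication rates 100% in both arms, because the background says "Postoperative ileus (POI) is one of the most common complications following abdominal surgery". The documents do not support this. The ileus is the entry condition and has its own timed item, no any-complication composite is defined, and nothing says the entry condition is scored. An explicit exclusion would still remove the doubt.

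Nor should one infer that a leak before Entereg can never be told from one after it. The information is said to be in the medical chart, so a date could be retrieved. The narrower statement holds: the listed data do not require that date.

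Finally, the affected outcomes are secondary, no power is claimed for them, and on the assumed 20% v 30% power is low (28%) even without dilution. That limits the weight of the point but does not answer it. A window that begins at assignment can be applied only if each event has a date.

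**Conclusion.** The point holds as a gap in data collection and outcome definition. The plan does not say when the morbidity, complication and reoperation outcomes start, and it does not require an onset date for ordinary complications. A dataset built from the lists cannot apply the post-enrolment window that the calendar suggests.

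If earlier events were counted, a true difference would shrink by the factor (1 − q): from 10 points to 9, 8 or 7 at q = 10%, 20% or 30%. The proportional shrinkage depends only on q; the rates and the independence of earlier and later events are assumptions. No systematic advantage to either arm follows from this. Open-label attribution of undated events after the fact could become differential, but nothing in the documents shows that it would. Mortality, readmission and the length-of-stay primary outcome are outside the point. It is a cheap improvement, worth making mainly because safety is part of the primary objective.

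**What to change.** 1. In Data to be collected and in Variables/Time Points of Interest, add the onset date and time of every complication, infection or leak, and reoperation, whether or not the event is reportable. Record the date and time of randomisation alongside.
2. In Study Overview, define the morbidity, complication and reoperation outcomes as events with onset after randomisation and up to the stated end of follow-up, and state the origin of the 30-day window.
3. In the Study Calendar, tick the complications row under Screening. Record earlier events, including the qualifying ileus, as baseline and report them separately by arm.

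The cost is one date field per event from the chart, one calendar tick and one outcome definition. Fewer events will be counted, and the rates will be less comparable with 30-day rates counted from surgery elsewhere; a supplementary table on that basis covers this. Treatment, eligibility and sample size do not change.

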Randomization will take place following enrollment and consent. A numbered, sealed envelope, corresponding to the patients' assigned study number, will be opened by *the study coordinator* indicating to which study group the patient is randomized. The study coordinator will notify the pharmacy which study group the patient has been randomized to. Randomization will be stratified to open or laparoscopic surgery, location of surgery (right/left), stoma reversal and presence or absence of stoma. *This will be kept in a locked key to be revealed at the end of the study.*

Enhanced Recovery After Surgery Pathway

All patients will be managed via standardized accelerated postoperative recovery guidelines, which are currently in use by the division of colorectal surgery at UHCMC. This includes patient-controlled analgesia pump, oral analgesia and diet on the first postoperative day, early postoperative ambulation, and defined discharge criteria.

Study Methods

At the time of diagnosis of postoperative ileus and after enrollment and randomization, all patients will be returned to NPO status. Nasogastric tubes (NGT) may be placed for gastric decompression at the discretion of the surgical team if clinically indicated. In the event that an NGT is placed, medications will be given orally or via the NGT, which will be clamped for 30 minutes after administration. Patients will continue on standard ERAS pathways with the exception of reduction of diet. Antiemetics will be given as clinically indicated; however, no prokinetic or promotility agents will be given as scheduled dosages.

Patients randomized to the study group will be given 12mg of Entereg orally twice a day, from the time of diagnosis of postoperative ileus to the time of return of bowel function and tolerating solid food without vomiting or experiencing significant nausea within 4 h following the meal, or without having to revert to enteral fluids only or for 5 days.

Patients randomized to the control group receive standard postoperative care.

The patient and surgical team will be able to know which arm of the study the patient is in based on documentation in the medical record of the administration of Entereg.

Patients in both groups will remain NPO until the return of bowel function, defined as passage of stool, decrease in nasogastric tube output. At this point, the nasogastric tube will be removed and a trial of oral diet will be attempted per surgeon's discretion.

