- Intraoperative IV fluids given
- Conversion from laparoscopic to open procedure
- Stoma creation
- Time/day surgery to ileus
- Time from surgery to medication given
- Time from ileus diagnosis to medication given
- Was there return of bowel function (flatus or stool, solid or liquid, stoma output) prior to ileus
- Intra-abdominal infection/anastomotic leak
- Time/day of return of bowel function post ileus (flatus and stool- solid or liquid, and stoma function)
- Time/day of ability to tolerate oral diet (liquid and solid food)
- Nasogastric tube placement and daily output
- Duration of nasogastric tube
- Total number of Entereg doses given
- Post operative complications including reoperation
- Length of stay in hospital, defined as time from surgery to discharge
- 30-day readmissions

Statistical Methods

The study co-investigators and research team will perform statistical analysis. Routine statistical analyses will be utilized for parametric and non-parametric datasets, as appropriate. Demographic data will be analyzed using students t-test or Fishers exact test as appropriate. Categorical data will be analyzed using χ^2 analysis or Fishers exact test where applicable. Normally distributed data will be presented as means \pm SD of the mean, non-normally distributed data will be presented as medians \pm quartiles and categorical data will be presented as raw data and frequencies. A p value of < 0.05 will be considered statistically significant.

Power/Sample Size:

In our practice, patients undergoing open or laparoscopic colectomy without stoma creation who develop POI have a mean length of stay of 10.67 +/- 5.98 days compared to 4.86 days for patients who do not develop POI.

Using this information, to detect a significant decrease in length of stay by 3 days, with a 0.05 level of significance and a power of 80%, a total of 142 patients (71 patients per arm) are required.

Drug supplies (Entereg) for this study will be provided by Merck.

In the event that Merck is unable to provide drug supplies, the University Hospitals Case Medical Center Pharmacy will provide Entereg for this study.

The University Hospitals Case Medical Center Pharmacy will be responsible for distribution of drug in the treatment arm.

All adverse events will be reported per local IRB policy.

Reportable Problem: Any event which meets all three of the following criteria:

- Unexpected (in relation to the protocol and informed consent document),

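### Length of stay is counted from surgery but patients are randomised later, at ileus diagnosis, so days the drug cannot affect add avoidable noise to the primary comparison

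*Combined protocol and SAP*

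**What the plan says.** The Study Overview states: "Primary outcome will be hospital length of stay". The outcome is defined only in the data lists (Data to be collected, repeated under Variables/Time Points of Interest), as "Length of stay in hospital, defined as time from surgery to discharge".

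Allocation comes later. The Study Overview says of eligible patients that "they will be randomized at the time of diagnosis of postoperative ileus", and the Randomization section adds: "Randomization will take place following enrollment and consent". Under Study Methods, Entereg is given "from the time of diagnosis of postoperative ileus to the time of return of bowel function" (the section adds further conditions), so no drug effect is possible before diagnosis.

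The interval before allocation is on both data lists as "Time/day surgery to ileus", but no analysis uses it. It is not a stratification factor: "Randomization will be stratified to open or laparoscopic surgery, location of surgery (right/left), stoma reversal and presence or absence of stoma". Statistical Methods names routine parametric and non-parametric tests and no covariate-adjusted model. No measure of stay from randomisation is listed, even as a sensitivity analysis.

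**The concern.** Write length of stay as T1 + T2, where T1 runs from surgery to ileus diagnosis and T2 from there to discharge. T1 is complete before allocation, so Entereg can act only on T2. An unadjusted comparison of T1 + T2 keeps all the variation in T1, and any chance difference between arms in mean T1 goes straight into the estimated effect.

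T1 can be expected to vary. Eligibility covers open and laparoscopic colorectal resection, small bowel resection and ileostomy reversal, and ileus may be declared either on return to nil by mouth after diet attempts or on nasogastric tube placement.

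Length of stay is the only outcome the trial is powered for. The Clinical hypotheses section concerns giving the drug after ileus has developed, and the days before that carry no information about its effect.

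**Working it through.** **Inputs.** From Power/Sample Size: SD of length of stay 5.98 days, target difference 3 days, significance level 0.05, power 80%, 71 per arm. Sidedness is not stated; two-sided is assumed. The SD of T1 is not in the documents; 1, 1.5, 2 and 3 days are assumed.

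**The plan's own figure.** The normal approximation gives n per arm = 2 × (1.960 + 0.842)² × 5.98² / 3² = 62.4, so 63 per arm (126 in total). The t-test needs 64 per arm (128). The stated 142 does not follow directly from the stated inputs. An unstated allowance of about 10% for dropout would explain it (64 × 1.10 ≈ 71). That is a separate matter and does not affect this point.

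**Power as planned.** The standard error of the difference is 5.98 × √(2/71) = 1.00 day. Power for 3 days at 71 per arm is 84.3% by the t-test (84.8% by the normal approximation).

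**Removing T1, with T1 and T2 uncorrelated.**
- SD(T2) = √(5.98² − SD(T1)²)
- Share of variance = SD(T1)² / 5.98²
- Standard error of the chance difference between arms in mean T1 = SD(T1) × √(2/71)

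| Assumed SD(T1), days | Share of variance | SD left, days | t-test power at 71 per arm | SE of T1 imbalance, days | 1.96 × SE, days |
|---|---|---|---|---|---|
| none removed | – | 5.98 | 84.3% | – | – |
| 1 | 3% | 5.90 | 85.3% | 0.17 | 0.33 |
| 1.5 | 6% | 5.79 | 86.6% | 0.25 | 0.49 |
| 2 | 11% | 5.64 | 88.3% | 0.34 | 0.66 |
| 3 | 25% | 5.17 | 92.9% | 0.50 | 0.99 |

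**Allowing for correlation ρ between T1 and T2.** SD(T2) now solves 5.98² = SD(T1)² + SD(T2)² + 2ρ·SD(T1)·SD(T2). With T1 as a covariate, the residual SD is SD(T2) × √(1 − ρ²). For SD(T1) = 2 days:

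| ρ | SD(T2), days | Power, clock moved only | Residual SD with T1 as covariate, days | Power with covariate |
|---|---|---|---|---|
| −0.3 | 6.27 | 80.8% | 5.98 | 84.4% |
| 0 | 5.64 | 88.3% | 5.64 | 88.3% |
| +0.3 | 5.07 | 93.9% | 4.83 | 95.7% |

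Moving the clock without adjusting can therefore lose power when ρ is clearly negative. Adjusting for T1 was no worse than the planned comparison anywhere in the range tried (SD(T1) 0.5 to 4 days, ρ from −0.3 to +0.3).

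**Same estimate from either clock.** In a linear model containing T1, replacing the outcome T2 by T1 + T2 adds exactly 1 to the coefficient of T1 and leaves the treatment coefficient unchanged. This requires T1 to end at the moment T2 begins.

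**The case against.** The strongest reply is that nothing here is invalid. T1 is fixed before allocation and balanced in expectation, so the unadjusted comparison is unbiased with the correct type I error. The added variance and the chance imbalance are one phenomenon, already inside the 1.00-day standard error. The planning SD of 5.98 days appears to be on the total-stay scale, so the noise has been budgeted for, and 71 per arm gives more than the stated 80% power. All of this stands. The loss is relative to a better analysis, not a shortfall against the plan.

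The size is also uncertain. Under the recovery pathway diet starts on the first postoperative day, and patients without ileus stay 4.86 days on average, so T1 may be fairly narrow. If it were uniform over days 1 to 5, its SD would be 4/√12 = 1.15 days and power would be about 85.7%. Nothing in the documents supports an SD of 3 days. This stands too, and it limits the magnitude.

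Total stay is a legitimate outcome, since the hypothesis names shorter hospital stay. If the adjusted estimate is the same from either clock, the origin may seem not to matter. But that identity holds only in a linear model that includes T1, and the plan has none. Under the non-parametric tests the plan allows, the choice of origin does matter.

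Finally, diagnosis and randomisation are not the same instant, and randomisation time is on neither data list. That is correct, and the fix has to provide for it.

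**Conclusion.** The concern holds. The primary outcome starts at surgery, allocation takes place at ileus diagnosis, and nothing in the design or analysis removes the days in between. The consequence is lost precision and exposure to chance imbalance, not bias.

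The gain available is about 1 percentage point of power if the SD of the interval is 1 day, and about 2, 4 or 9 points at 1.5, 2 or 3 days. This assumes zero correlation with later stay, a two-sided t-test, a 3-day effect and a total SD of 5.98 days. A positive correlation would increase the gain. At a correlation of −0.3 and an SD of 2 days it is essentially nil with adjustment. The mismatch is certain from the text; its size is not. The plan should be changed because the remedy costs almost nothing, but the trial does not fail without it.

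**What to change.** Define the primary outcome as time from randomisation to discharge, and prespecify time from surgery to randomisation as a covariate in the primary model. Do not move the clock without the covariate. Report surgery-to-discharge stay descriptively. State that time to return of bowel function also starts at randomisation; the data lists refer to return after ileus but give no clock start.

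Record the date and time of randomisation for every patient. If that is not possible, use ileus diagnosis as the boundary for both the outcome and the covariate, in both arms.

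The cost is one sentence in the outcome definition, one model term and one added field. Time from surgery to ileus is already collected, and no extra patients are needed. If the sample size is restated for the new outcome, it needs an SD on that scale, which the documents do not give; until then 5.98 days can stand as a planning value, though a clearly negative correlation would raise the SD of the unadjusted outcome slightly above it.

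Make the change before outcome data are examined. Patients and surgical team can know the allocation, and the study team does the analysis, so a clock or covariate chosen later could look data-driven.
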